11.2.4 Other variables

Quality of Life endpoints

The Quality of Life endpoints are defined in Section 6.4.

- Change from baseline to Week 12 and Week 24 in LSS for chronic GVHD [Appendix 8]
- Change from baseline to Week 12 and Week 24 in each of the subject-reported chronic GVHD symptoms (skin, eyes, mouth and genitals [Appendix 7 – Form B]).
- Change from baseline to Week 12 and Week 24 in each of the subject-reported global ratings (Mild-Moderate-Severe Scale, Overall Severity Scale and 7-Point Change Scale [Appendix 7 – Form B]).

PK evaluations

- C_{trough} concentrations of ponesimod at Day 1, and Weeks 4, 8, 12, 16, and 20 (all samples pre-dose), and Week 24
- Ponesimod concentration 3 hours post-dose at Day 1 and Week 12

PD evaluations

- Peripheral absolute blood lymphocyte count change from baseline (pre-dose on Day 1) to Weeks 4, 8, 12, 16, 20, 24, and FU1, and change from pre-dose Week 12 to 3 hours post-dose Week 12.
- Peripheral absolute lymphocyte count reversibility from EOT1 to FU1 all expressed in absolute change and percent change from baseline

PK/PD relationship

- The PK and selected efficacy and safety variables will be correlated with the PD (peripheral absolute lymphocyte count and magnitude of reduction of lymphocyte count). If deemed appropriate, the PK will also be correlated with selected safety variables.

11.2.5 Variables in Extension Treatment Period

Variables in the Extension Treatment Period will be defined in the same way as defined in the treatment and follow-up periods of the Core Treatment Period and will be fully described in the SAP. As the Extension Treatment Period exceeds the Core Treatment Period by 72 weeks the time points of analysis will be adapted appropriately for all relevant endpoints. The visit EX-1 (Visit 11) will be considered as the baseline visit in the Extension Treatment Period.

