	
Systemic glucocorticoids (Core Treatment Period only)
 
Glucocorticoid dosing should not be increased or decreased during the course of the study, with the following exceptions:
 
• The investigator may see reason to initiate or increase the dose of systemic glucocorticoid to treat chronic GVHD flare or another condition. In this case, the investigator should consult with the sponsor prior to initiation or dose increase and the reason for dose increase should be documented. The subject may continue on ponesimod. The prednisone-equivalent dose should never exceed 1 mg/kg/day.• Systemic glucocorticoid dosing may be lowered to avoid or prevent short- and long-term glucocorticoid toxicity. For subjects on longer term glucocorticoid therapy, it is recommended that the dose reduction rate does not exceed 10% of the dose per week. Glucocorticoid dosing may be increased following reduction, if medically indicated.• Systemic glucocorticoid dosing is not subject to restrictions during the Extension Treatment Period. 
Mandatory systemic IS other than ponesimod or systemic glucocorticoids (Core Treatment Period only)
 
Systemic IS dosing (mg daily dose) should not be increased above baseline dose during the course of the study, with the following exception:
 
• Systemic IS blood or serum level is below the therapeutic range that was defined for the subject at the time of entry into the study. The dose should be increased to restore blood or serum levels to within the defined therapeutic range. (IS that are not monitored with blood or serum level monitoring may never be increased above baseline dose.) 
Systemic IS dosing (mg daily dose) should not be lowered during the course of the study, with the following exceptions:
 
• Adverse event (AE) or intolerance due to the systemic IS. The dose should be sufficiently lowered or discontinued, per investigator judgment.
--	--

Confidential

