Subjects successfully completing the initial 24 week treatment period (i.e., subjects not prematurely discontinued from study drug) are followed for 90 days after stopping study drug. Should subject's chronic GVHD progress after stopping ponesimod, they may restart ponesimod 7 to 90 days later. The rationale for the timeframe to restart is based on the following data:

- Previous experience in humans shows that lymphocyte counts recover within 7 days of stopping ponesimod [Ponesimod IB, section 1.4]. (It would be difficult to attribute progression of chronic GVHD to cessation of ponesimod's effect during the first 7 days after stopping, and difficult to justify restarting ponesimod in that period for that reason).
- Previous experience in chronic plaque psoriasis patients suggests that the proportion of patients with relapse of psoriasis approaches a plateau within 12 weeks after cessation of ponesimod [figure 2 in Vaclavkova 2014].

Subjects may be retreated with ponesimod for 96 weeks. There is limited data to support a rationale for duration of therapy of an investigational agent in responders. However, resolution of chronic GVHD is known to occur slowly, with many patients requiring several years of immunosuppressive therapy [Martin 2009].

The 96 week Extension Treatment portion of the study will thus continue to make study drug available for subjects who were previously shown to benefit from ponesimod. This extended treatment period will also provide longer term safety, tolerability and efficacy data. In contrast to the initial 24 week treatment period, investigators will have greater flexibility in administering allowed concomitant background immunosuppressant therapy.

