4.6 Extension Treatment Period inclusion criteria

For inclusion into the Extension Treatment Period of the study, all of the following inclusion criteria must be fulfilled. No waivers of any of the criteria for any subject are allowed:

1. Signed informed consent prior to initiation of any study-mandated procedure.
2. Subject has completed the 24 weeks of treatment of the Core Treatment Period and the EOT1 visit.
3. Subject has experienced disease progression 7 to 90 days after EOT1 visit, versus EOT1 chronic GVHD activity assessment, for at least one previously involved organ. Progression is per NIH Consensus Development Project response criteria and is defined in Section 6.3.2.
4. WOCBP, as defined in Section 4.3.1, must have a negative urine pregnancy test at enrollment visit EX-1, and at all prior visits, and must agree to undertake monthly scheduled urine pregnancy tests during the study and up to the protocol defined EOS.
5. WOCBP must agree to use acceptable MOC during the study and up to the protocol defined EOS.

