6.3.2 Partial overall response definition

A partial overall response is defined as improvement in a measure for at least one organ without increase in measures for any other organ. A subject is considered as a partial responder at the Week 24 assessment, if there is a change of clinical benefit from baseline in at least one of the organs assessed (skin, mouth, liver, upper and lower GI, esophagus, lung, eye, and joint/fascia) and no progression in any other organ (stable NIH scores compared to baseline).

The proposed general guideline for defining partial response in a specific organ requires a change in score from baseline as follows:

- Skin: decrease in NIH Skin Score by at least 1 point
- Mouth: decrease in NIH Modified Oral Mucositis Score by at least 2 points
- Liver: decrease by 50% in ALT, alkaline phosphatase, or TBL
- Upper GI: decrease in NIH Upper GI Score by at least 1 point
- Lower GI: decrease in NIH Lower GI Score by at least 1 point
- Esophagus: decrease in NIH Esophagus Score by at least 1 point
- Lungs: increase by at least 10% predicted absolute value of FEV₁, as long as initial FEV₁ < 70% predicted
- Eyes: decrease in NIH Eye Score by at least 1 point
- Joint/fascia: decrease in NIH Joint and Fascia Score by 1 or more points or increase in P-ROM score by 1 or more points for any site
- Global: Clinician Overall Severity Score decreases by 2 or more points on a 0–10 scale

The proposed general guideline for defining progression in a specific organ requires a change in score from baseline as follows:

- Skin: increase in NIH Skin Score by at least 1 point, except from 0 to 1
- Mouth: increase in NIH Modified Oral Mucositis Score by at least 2 points
- Liver: increase by $\geq 2 \times$ ULN for ALT, alkaline phosphatase or TBL
- Upper GI: increase in NIH Upper GI Score by at least 1 point, except from 0 to 1
- Lower GI: increase in NIH Lower GI Score by at least 1 point, except from 0 to 1

- Esophagus: increase in NIH Esophagus Score by at least 1 point, except from 0 to 1
- Lungs: decrease by at least 10% absolute value of FEV₁, as long as final FEV₁ < 70% predicted
- Eyes: increase in NIH Eye Score by at least 1 point, except from 0 to 1
- Joint/fascia: increase in NIH Joint and Fascia Score by 1 or more points or decrease in P-ROM score by 1 or more points for any site
- Global: Clinician Overall Severity Score increases by 2 or more points on a 0–10 scale

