Spirometry testing will be performed by a PFT technician, respiratory therapist or expert, or an equally experienced person according to the ATS/ERS guidelines [Miller 2005a] (e.g., for US, registered pulmonary function technologist and/or registered respiratory therapist). To the extent logically feasible, attempts should be made to have the same tester throughout the study for a subject, and this information will be recorded in the eCRF. Back-up testers (PFT technician, respiratory therapist, or expert or an equally qualified person according to the ATS/ERS guidelines [Miller 2005a]) may conduct spirometry if the primary tester is not available. All PFT technicians or other qualified persons participating in the studies will be trained on the specific requirements for the studies and have refreshment on ATS/ERS recommendations before study start and when compliance issues are identified.

Confidential

Subjects must refrain from taking short-acting β_2 agonists (i.e., salbutamol) for 6 hours and long-acting β_2 agonists for 24 hours prior to spirometry testing. To perform the spirometry test, subjects will be rested for a minimum of 5 minutes prior to start. Sufficient forced expiratory maneuvers (up to a maximum of eight) will be performed to produce a minimum of three technically acceptable and repeatable traces (according to ATS/ERS guideline criteria). The best (largest) FEV₁ and FVC values from the three acceptable and repeatable tests are to be selected by the PFT technician and recorded in the eCRF and will serve for the calculation of % of predicted values and used for the endpoint derivations. These values may come from separate maneuvers. The FEV₁ and FVC measures obtained at Visit 2 (Day 1) and selected as described above will be used as the study baseline.

PFT values that trigger study drug discontinuation are described in Section 5.1.10.7. Clinically relevant findings meeting the definition of an AE (new AE, or worsening of previously existing condition) [see Section 10.1.1] must be recorded on an AE page of the eCRF.

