11.2.9 Analysis of the efficacy variables during the Extension Treatment Period

The analyses of all exploratory endpoints will be based on the ES.

All efficacy variables will be summarized descriptively, by visit, based on the ES. If subject numbers drop below a certain threshold only listings will be provided. No statistical tests will be applied to any of these endpoints.

Confidential

The endpoint “Achievement of a partial or complete overall response at 24 weeks (per NIH Consensus Development Project response criteria)” will be analyzed at Week 24 and Week 96 in the Extension Treatment Period and selected other time points.

The endpoint “Need for rescue therapy for chronic GVHD” will be analyzed throughout 96 weeks of treatment or up to premature discontinuation.

The endpoint “Partial or complete organ-specific response for the specific organ manifestation at Week 12 and Week 24 in subjects with a specific organ manifestation of chronic GVHD” will be assessed at Weeks 12, 24, and 96 in the Extension Treatment Period and selected other time points.

The endpoint “Partial or complete overall response at Week 12” will also be analyzed at Week 12 in the Extension Treatment Period.

The endpoint “Complete response at Week 24” will be assessed at Week 24 and Week 96 in the Extension Treatment Period and selected other time points.

The endpoint “Partial or complete overall response at latest evaluable assessment during the study” will be extended to the whole Extension Treatment Period.

The exposure related endpoints will be analyzed based on summary statistics. Both endpoints “Percent glucocorticoid dose at Week 24 versus baseline” and “Average glucocorticoid daily dose over 24 weeks versus baseline dose” will be analyzed at the end of treatment visit (EOT2) in the Extension Treatment Period, and compared to the baseline visit of the Extension Treatment Period (Visit EX-1).

If there are not enough subjects in the ES population, only listings will be provided.

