11.2.10.4 Pulmonary safety

11.2.10.4.1 PFT

Descriptive summary statistics by visit will be provided for observed treatment-emergent values and changes from baseline by visit in FEV₁, FVC and FEV₁/FVC ratio (all expressed in absolute change, % change and % change of percent predicted value).

The number and proportions of treatment-emergent decreases of FEV₁ or FVC and percent predicted FEV₁ or FVC > 20% from baseline up to Week 24 will be summarized.

Reversibility of pulmonary parameters will be analyzed at the last available follow-up visit. The analysis will summarize subjects still showing a decrease of > 200 mL in FEV₁ and FVC or a change in FEV₁ and FVC of > 12% from baseline at the follow-up visit among subjects with a decrease of > 200 mL or > 12% in FEV₁ or FVC from baseline to EOT1.

The mean (and 95% CIs) change from baseline to FU1 and from baseline to EOT1 in FEV₁ or FVC (absolute and % predicted) will be summarized and plotted. A scatter plot will display the change from baseline to EOT1 versus the change from baseline to FU1 on an individual subject level.

PFT data will be analyzed in a similar manner during the Extension Treatment Period.

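### EX-1 is the only Extension baseline; add Core Day 1 as a second reference for NIH response and lung change

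*Combined protocol and SAP*

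**What the plan says.** - **Baseline.** Section 11.2.5 defines Extension variables as in the Core period and adds: "The visit EX-1 (Visit 11) will be considered as the baseline visit in the Extension Treatment Period". It leaves full definitions to the SAP; the supplied document holds no separate SAP text. Section 11.2.9 gives Extension time points for NIH response, names no other reference, and uses EX-1 again for the two glucocorticoid endpoints.
- **Entry.** Section 4.6, criterion 3: "Subject has experienced disease progression 7 to 90 days after EOT1 visit, versus EOT1 chronic GVHD activity assessment", in at least one previously involved organ. A Core response is not required. Section 3.3 nevertheless describes the Extension as making "study drug available for subjects who were previously shown to benefit from ponesimod", and says that it will provide longer-term safety, tolerability and efficacy data.
- **Response and progression.** Section 6.3.2 defines both as change from baseline. For skin, progression is "Skin: increase in NIH Skin Score by at least 1 point, except from 0 to 1", and partial response is a fall of at least 1 point.
- **Lung.** Section 7.3.3 says that the FEV1 and FVC "measures obtained at Visit 2 (Day 1) and selected as described above will be used as the study baseline". Section 11.2.10.4.1 says "PFT data will be analyzed in a similar manner during the Extension Treatment Period", and 11.2.10.4.2 treats DLco likewise. The event of a fall of more than 20% in FEV1 or FVC carries over to the Extension (11.2.10.4.3).
- **Background therapy.** Section 5.2.2: "Systemic glucocorticoid dosing is not subject to restrictions during the Extension Treatment Period".

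**The concern.** A subject arrives at EX-1 because the disease worsened after ponesimod was stopped. If every Extension change is counted from there, a return to the EOT1 state scores as response. A reader of the Extension response rate then cannot separate subjects who are better than at study entry from those who have only recovered the flare that qualified them.

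The lung issue is the same in form and matters more for safety, because pulmonary function decline is a known effect of ponesimod (1.3.2.4). Loss that has accrued between Day 1 and EX-1 becomes the new zero. The protocol expects the drug's own effect to reverse within a few days of stopping (5.1.10.7), and EX-1 falls at least 7 days after EOT1. What remains at the EX-1 pre-dose test is therefore mainly loss that has not reversed, and that is the part a long-term summary should show.

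**Working it through.** The plan gives no figure for Extension response or Extension lung events, so there is none to reproduce. The values in steps 1 and 2 are assumed for illustration; the rules are the protocol's.

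**1. NIH response.** Apply 4.6, 6.3.2 and 6.3.3 to one skin-score path, with all other organs stable.

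| Comparison | Scores | Change | Classification |
|---|---|---|---|
| Day 1 to EOT1 | 2 to 2 | 0 | Core non-responder (stable) |
| EOT1 to EX-1 | 2 to 3 | +1 | Progression; may enter the Extension |
| EX-1 to Extension Week 24 | 3 to 2 | -1 | Partial responder under 11.2.5 |
| Day 1 to Extension Week 24 | 2 to 2 | 0 | Stable, hence non-responder |

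The same can happen in other organs because the two thresholds in 6.3.2 are equal in size: 1 point for skin, eyes, esophagus, upper GI, lower GI and joint/fascia, and 2 points for mouth. Rises from 0 to 1 are exempt from progression for skin, eyes and the three GI scores. The path also shows that a subject with no Core response can enter, contrary to the description in 3.3.

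**2. Lung events.** If EX-1 is already a fraction x below Day 1, a fall of 20% from EX-1 leaves (1 - x) × 0.80 of the Day 1 value, so the total loss is 1 - (1 - x) × 0.80:

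- x = 5%: 1 - 0.95 × 0.80 = 24%
- x = 10%: 1 - 0.90 × 0.80 = 28%
- x = 15%: 1 - 0.85 × 0.80 = 32%

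In litres: FEV1 of 3.0 (Day 1), 2.5 (EX-1) and 2.3 (later Extension visit).

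- Day 1 to EX-1: (2.5 - 3.0)/3.0 = -16.7%, not an event.
- EX-1 to the later visit: (2.3 - 2.5)/2.5 = -8.0%, not an event.
- Day 1 to the later visit: (2.3 - 3.0)/3.0 = -23.3%, an event, but not counted if EX-1 is the baseline.

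**3. Whether another planned output shows cumulative loss.**

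- *Core reversibility summary (11.2.10.4.1).* It uses the last available follow-up. FU1 is cancelled when EX-1 falls on or before its scheduled day (Table 1, note 8), and FU2 has no spirometry (Table 1; 8.3.2). An early re-starter therefore has no Core follow-up spirometry.
- *Core events of more than 20%.* They are counted from Day 1, but stop at Week 24 in 11.2.10.4.1, or at most 30 days after the last Core dose (11.2.10).
- *Bronchodilator rule (5.1.10.7).* It uses the study baseline and applies in the Extension (5.1.10), but it also requires FEV1 below 60% predicted and FEV1/FVC below 0.7. A subject at 75% predicted or more on Day 1 can lose 20% and not fall below 60% (0.80 × 75 = 60), taking the predicted value as constant.
- *Observed values by visit and listings (11.2.10.4.1; Section 11).* The raw data are there, but they give no subject-level change from Day 1.

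If 11.2.5 is applied as written, no planned change or event summary is sure to show loss since Day 1.

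**The case against.** The strongest reply is that EX-1 is the right baseline for the question the Extension asks. Drug is restarted because disease flared after stopping, and recovery of that flare is response to re-treatment. This stands, and it is why EX-1 should be kept.

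A reader might go further and infer that EX-1 inflates the response rate by a calculable amount through regression to the mean, and that Day 1 would give the unbiased figure. The documents do not support either step. Day 1 is itself selected: inclusion criterion 5c admits subjects who are progressing, or not improving, at enrolment. On the progression route this is the same kind of selection as Extension entry. Nor need EX-1 be the reading that qualified the subject. The synopsis treats the progression assessment and the restart as separate events within the 7- to 90-day window; Form A is also completed at FU1 and FU2, and again within 48 hours before EX-1 dosing (8.4.1). If an earlier visit qualified the subject, scoring error at EX-1 was not selected upon. The excess over a Day 1 reference may therefore be zero.

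On lung, one could say that nothing is unresolved: 11.2.5 sets the analysis baseline, and the study baseline of 7.3.3 serves the stopping rules. The two can coexist, so a reader should not infer a contradiction or a gap in individual safety monitoring. A pulmonologist reviews the results (3.4.6), and the bronchodilator rule refers back to Day 1. That reply does not supply the missing cumulative summary.

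Finally, complete response rests largely on reaching score 0 or normal values (6.3.1) and is little affected. Extension efficacy is descriptive and untested, and may be reduced to listings (11.2.9). The SAP may also add a reference. These points limit the importance of the concern but do not remove it.

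**Conclusion.** The point holds as a cheap improvement. With EX-1 as the sole baseline, a recovered flare counts as partial response without gain over study entry, and cumulative FEV1, FVC and DLco loss since Core Day 1 goes unsummarised, including for early re-starters whose FU1 is cancelled.

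The size cannot be derived. The documents give no scoring-error rate, no split between the two routes of criterion 5c, no proportion of subjects qualifying before EX-1, and no expected lung loss by EX-1. The 24%, 28% and 32% figures depend on assumed prior losses of 5%, 10% and 15%, and on EX-1 being the lung baseline as 11.2.5 states. The skin path shows that the classification can occur, not how often.

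The effect is confined to descriptive Extension summaries. The primary lymphocyte analysis and the Core results are unaffected. Neither baseline allows attribution to ponesimod, since the study is single-arm and background immunosuppression is unrestricted in the Extension.

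**What to change.** - **11.2.5 and 11.2.9:** keep EX-1 and label it the re-treatment baseline. Also report Extension NIH overall response versus Core Day 1.
- **11.2.10.4:** also report change in FEV1, FVC and DLco, and FEV1/FVC events of more than 20%, versus Core Day 1 (for FEV1 and FVC, the study baseline of 7.3.3), starting with the EX-1 pre-dose value.

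The data are already collected at Day 1 (8.1.2.1), at EX-1 (8.4.1) and at later Extension visits (8.4.3, 8.4.4), so there is no added burden on subjects. The cost is a few extra descriptive columns in a small exploratory analysis. A note should say that Day 1 is also a selected visit, so that the second reference is not read as free of bias.

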11.2.6 Overall testing strategy of the PD variable

The primary analysis of this study is based on the absolute lymphocyte counts at pre-specified time points. Hypotheses are setup to establish a within-subject dose response at baseline vs the Week 4 (5 mg), Week 8 (10 mg) and Week 12 (20 mg) assessments in the Core Treatment Period.

11.2.7 Analysis of the primary PD variable(s)

11.2.7.1 Hypotheses and statistical model

The null hypothesis is that there is no dose response on the change from baseline in absolute lymphocyte counts l_d in the intra-subject dose escalation within the first 12 weeks of

Confidential

treatment, and the alternative hypothesis is the existence of any intra-subject dose response within the first 12 weeks of treatment:

$$H_0: l_d \geq 0 \text{ for all doses } d = 5, 10, 20 \text{ mg}$$

vs

$$H_1: l_d < 0 \text{ for at least 1 dose } d = 5, 10, 20 \text{ mg}$$

